Appendix 4: Site-Specific Protocol Addendum Template

PURPOSE: The use of this site-specific protocol addendum is recommended with a multi-site study.

The purpose of this site-specific protocol addendum is to obtain information describing the local site-specific elements for conduct of the Core Protocol. The descriptions should focus on who, what, and where of the local study activities.

INSTRUCTIONS:

1. Add the Name of the study site to the Title of the Protocol in the header of the document.
2. Please complete each section below. If general description language already appears in the Core Protocol, which adequately describes the local activity at the study site, a notation can be inserted in the given section that reads, “As described in the Core Protocol.”
3. Please identify the completed addendum document using a version number and date.
4. Please note: the site-specific protocol addendum will require review and approval by the local Institutional Review Board (IRB)/Ethics Committee (EC) of record for the study site.

Study Site Information:

Name of Institution/Company:

Address:

Study Site Information for the Site Investigator:

Name of Site Investigator:

Title:

Institution/Affiliation:

Address:

Telephone Number:

Cell/Other Number:

Fax Number:

Study Site Number:**Assurance Information:**

United States Department of Health and Human Services Office for Human Research Protections
Assurance Federal Wide Assurance number:

Expiration Date:

IRB/Ethics Committee Information:

Name of Human Subjects Protection oversight office for study site:

Name and number of reviewing IRB/EC:

Telephone Number at Office:

Fax Number at Office:

If Available, Point of Contact at IRB/EC:

Name:

Telephone Number:

Local Site-specific Information:

1. Identify key study personnel (include name, title, address, point of contact information).
2. Describe the key study personnel roles and responsibilities.
3. Describe the local recruiting procedures and strategies. Provide copy of any site-specific recruitment material. Identification of personnel responsible for completing tasks.
4. Describe the local consenting process. Provide a copy of the site-specific consent form(s). If an Ombudsman is named for the study site, provide name, title, and point of contact information.
5. Identify local study collaborations at the site such as pharmacy, laboratories, and other institutional departments.
6. Describe the local specimen/sampling procedures in place. Include acquisition, disposition, storage, and unique coding. If samples will be kept for future use, describe procedures and the security measures for short-term and long-term management. Provide name of repository.
7. Describe the plan for on-site management of study records and data, and participant study records. Explain procedures and security measures in place for short- and long-term management. Declare who will have access to data.
8. Describe the local measures in place to promote privacy and confidentiality.
9. Describe the local procedures in place for provision of care for the participant regarding research-related injuries.
10. Identify who the participant can contact locally should the participant have any questions regarding the research. Identify who the participant can contact should the participant have questions regarding their rights as a study participant. Include the points of contact information (name, title, and telephone number).
11. Describe the procedures in place to address Health Insurance Portability and Accountability Act requirements. If a separate authorization form will be used at the

study site, provide a copy or ensure appropriate language has been included in the consent document(s).

12. Describe any unique site-specific study procedures or supplemental activities.
13. Declare any unique study population/cultural influences, socioeconomic conditions, etc.
14. Declare any other site-specific reporting obligations and procedures. Name any additional oversight boards or committees.
15. Define abbreviations that may apply to the specific study site.

Appendix 5: Hydroxychloroquine Label

Generic hydroxychloroquine label (current as of June 2018) is available online at <https://dailymed.nlm.nih.gov/dailymed/drugInfo.cfm?setid=b82bbda6-64f2-4426-b4ec-254eeea895ae> and provided below.

Appendix 6: Azithromycin Label

The Azithromycin label is available online at <http://labeling.pfizer.com/ShowLabeling.aspx?format=PDF&id=511> and provided below.

Appendix 7: Lopinavir-ritonavir Label

Kaletra (Lopinavir-ritonavir), US Prescribing Information, AbbVie, December 2019 is available online at <https://rsc.niaid.nih.gov/sites/default/files/Lopinavir-Ritonavir%20%28Kaletrata%29%20PI%20dated%20December%202019.pdf> and provided below.

Appendix 8: Physiologically Based Pharmacokinetic Model for Azithromycin Dose Regimen

A physiologically based pharmacokinetic (PBPK) model for azithromycin was developed previously and verified against clinical data (Johnson et al., 2016). With the exception of the B:P ratio, which was set at 2.28, the input parameters for the azithromycin model remained the same. This updated model was then used to predict exposures in plasma and lung after administration of 500 mg for 1 day and 250 mg QD for 4 days, a dosage regimen that was used by Gautret et al. (2020) to prevent bacterial super-infection in patients receiving hydroxyl-chloroquine as treatment for SARS-CoV-2. Based on physicochemical data, the predicted lung to tissue ratio (K_p) was 16.33, which was lower than the observed ratio of 50.5 (Lucchi et al., 2008). Both predicted and observed ratios were used in simulations (100 subjects aged 20 – 50 years; 50% female) of plasma and lung concentration-time profiles which were then compared against *in vitro* values of 2.12 (EC_{50}) and 8.65 μ M (EC_{90}) reported for inhibition of SARS-CoV-2 by azithromycin (Touret et al., 2020) (Figure 1). It should be noted that the unbound fraction in plasma (f_u) was set at 0.69 and the predicted f_u in lung tissue was 0.82. Thus, unbound and total concentrations were similar in both plasma and lung.

[figure not shown]

Figure 1. Predicted concentration-time profiles for azithromycin in the lung based on K_p values of 16.33 and 50 in the lung.

Based on the simulations shown, it appears that the dosing regimen of 500 mg for 1 day followed by 250 mg QD for 4 days, is able to attain concentrations of azithromycin in lung that would approach the *in vitro* EC_{50} value determined for azithromycin.

Gautret et al. (2020) Hydroxychloroquine and azithromycin as a treatment of COVID-19: results of an open-label non-randomised clinical trial. *International Journal of Antimicrobial Agents* – In Press 17 March 2020: – DOI : 10.1016/j.ijantimicag.2020.10594.

Johnson TN, Jamei M and Rowland-Yeo K (2016). How does in vivo biliary elimination of drugs change with age? Evidence from in vitro and clinical data using a systems pharmacology approach. *Drug Metab Dispos*; 44:1090-1098.

Appendix 9: Pharmacokinetic Sample Collection and Analysis

Collection of Blood

Skin puncture

1. Put on a pair of disposable gloves.
2. Before skin puncture, the participant should warm his/her hands. The finger is massaged anterogradely to enrich the blood flow toward the puncture site.
3. Clean the skin of the palmar side of the tip of the distal phalanx of the third or fourth finger of the nonwriting hand with a suitable disinfectant, for example, 70% isopropyl alcohol. Puncture the skin by a single-use safety lancet. The finger should be held in such a position that the gravity facilitates the collection of blood from the fingertip.
4. When collection of capillary blood by skin puncture is complete, place a bandage on the fingertip.

Venipuncture

To be conducted by trained personnel per standard procedures.

Preparation of Blood Spots

Preparation from blood collected by skin puncture

1. Wipe off the first drop of blood with a gauze pad because it may contain excess tissue fluids. Massage the finger again to increase blood flow at the puncture site. Transfer the following drop to one of the circles of a filter card without touching the surface directly with the fingertip. Allow the blood to be soaked into the texture of the filter by capillary forces only.
2. Let the next large drop of capillary blood form on the fingertip and collect it in the next circle. Continue this procedure until all necessary circles are filled or blood flow stops.
3. Do not squeeze or “milk” the finger excessively if the blood flow is not sufficient to fill all the required circles of the filter card. If blood flow stops, place a bandage on the fingertip. Perform a second skin puncture on another finger if more blood is needed for the examination.
4. For blood obtained by venipuncture, use syringe to apply approximately 100 μ L of blood on the filter paper.

Drying of Blood Spots

To dry the blood spots, put the filter cards on a clean paper towel and let them dry, preferably overnight (but for at least 4 hours), at room temperature in the absence of any external source of heat. When the drying process is complete, the blood spots have a uniformly dark brownish color and no red areas are visible anymore.

Storage and Transportation of Dried Blood Spots

NOTE: Processing of the blood spots can be interrupted after drying. The filter cards can now be stored.

1. For storage, put the filter paper card in a single, gas-impermeable zipper bag, containing 1 to 2 desiccant sachets to protect the specimens from moisture. Optionally, add a humidity indicator card.
2. Transfer this bag to a freezer as soon as possible. If freezers are not available under field conditions, storage at -4°C or even at ambient temperature is feasible for up to 14 days.
3. Transport frozen dried blood spots specimens on dry ice. For filter cards initially kept at ambient temperature, use a triple packaging system, which consists of the zipper bag(s) as the inner container(s) as well as an inner and an outer envelope. No content markings are required on the outer envelope for shipment by regular mail, but the international biohazard symbol must be affixed to the primary inner container.
4. Exclude the filter cards from further processing if the desiccant packs and/or the additional humidity indicator card changes to a pink color.

On the filter paper, the participant should record the following:

1. Date of collection

Samples that appear to be collected according to the schedule of activities, which have the required amount of blood for a 5- to 6-mm punch and have the minimal required information (1 through 3 above), will be processed for hydroxychloroquine (and metabolite) and azithromycin concentration.

Appendix 10: Physiologically Based Pharmacokinetic Modeling of Hydroxychloroquine Used for Post-exposure Prophylaxis

Appendix 11: WHO Ordinal Scale for Clinical Improvement

WHO COVID-19 Core Protocol
SOLIDARITY Trial
Version 10.0, March 22, 2020

Patient State	Descriptor	Score
Uninfected	No clinical or virological evidence of infection	0
Ambulatory	No limitation of activities	1
	Limitation of activities	2
Hospitalized Mild disease	Hospitalized, no oxygen therapy	3
	Oxygen by mask or nasal prongs	4
Hospitalized Severe Disease	Non-invasive ventilation or high-flow oxygen	5
	Intubation and mechanical ventilation	6
	Ventilation + additional organ support – pressors, RRT, ECMO	7
Dead	Death	8

Appendix 12: The inFLUenza Patient-Reported Outcome instrument (Flu-PRO) – Modified for SARS-CoV-2

DAILY SURVEY (D1-14, D21, D28)

inFLUenza patient-reported outcome (Flu-PRO): 32 items validated, can score across domains.

***FYI: This takes about 5 minutes to complete

How are you feeling today?

FLU-PRO	Not at all	A little bit	Somewhat	Quite a bit	Very much
---------	------------	--------------	----------	-------------	-----------

Nose

- Runny or dripping
- Congestion or stuffy
- Sneezing
- Sinus pressure
- Lack of smell

Throat

- Sore throat
- Scratchy or itchy throat
- Difficulty swallowing
- Lack of taste

Eyes

- Teary or watery eyes
- Sore or painful eyes
- Eyes sensitive to light

Chest/Respiratory

- Trouble breathing
- Chest congestion
- Chest tightness
- Dry or hacking cough
- Wet or loose cough

Sputum (coughing up sputum or phlegm)

Wheezing

Gastrointestinal

Felt nauseous

Stomach ache

Vomit

Diarrhea

Body/Systemic

Felt Dizzy

Head congestion

Headache

Lack of appetite

Sleeping more than usual

Body aches or pains

Weak or tired

Chills or shivering

Felt cold

Felt hot

Sweating

How are you feeling today?

0 no symptoms 1 Mild 2 Moderate 3 Severe 4 Very severe

Please rate interference in daily activities due to illness:

1 Not at all 2 A little bit 3 Somewhat 4 Quite a bit 5 Very much

How is your general health?

1 Poor 2 Fair 3 Good 4 Very good 5 Excellent

Have you returned to your usual health today? Yes/no

Have you returned to your usual activities today? Yes/no

TAKE MEDS, TAKE SWAB (Copy post-exposure prophylaxis)

Take your vitals:

- Oxygen level
- Pulse
- Temperature
- Respiratory rate
- Electrocardiogram monitor

PM Time:

- Take meds
- Take vitals
- Oxygen level
- Pulse
- Temperature
- Respiratory rate

Anxious mood Not at all mild moderate severe very severe

1. INTRODUCTION

This version of the SAP focuses on the three arms first implemented in the protocol.

1.1. GENERAL DESIGN CONSIDERATIONS

1.2. STUDY OBJECTIVES AND ENDPOINTS

The protocol was written early in the pandemic when there was not adequate information about typical disease course. Between then and the writing of this document, our understanding of COVID-19 disease progression has changed, resulting in changes to some of the objectives and endpoints. Most notably, the trial was stopped early for operational futility on the primary clinical objectives. These changes are noted in the table below.

Table 1 Original objectives and endpoints as written in the protocol

Objectives	Endpoints
Primary	
To test the efficacy of HCQ and HCQ + azithromycin compared to placebo to prevent progression to LRTI, among persons with SARS-CoV-2 infection who are at high risk of progression	LRTI, defined by resting SpO ₂ <93%, sustained for 2 readings 2 hours apart AND presence of subjective dyspnea or cough
To test the efficacy of HCQ and HCQ + azithromycin compared to placebo to prevent hospitalization and death measured at Day 28 among participants who are at high risk of progression	Cumulative incidence of hospitalization or mortality, measured at Day 28
To test the efficacy of HCQ and HCQ + azithromycin compared to placebo to reduce SARS-CoV-2 viral shedding	Time to clearance of nasal SARS-CoV-2, defined as 2 consecutive negative swabs (swabs collected daily Day 1 through Day 14)
Secondary	
1. To test the safety of HCQ and HCQ + azithromycin compared to placebo for	Serious adverse events (including death and hospitalization) and adverse events resulting in treatment discontinuation

treatment of high-risk outpatients with SARS-CoV-2 infection	
2. To test whether HCQ and HCQ + azithromycin has an effect on the duration of hospitalization among persons who become hospitalized with COVID-19 disease	Days of hospitalization
3. To test whether HCQ and HCQ + azithromycin has an effect on disease severity compared to placebo	
 Peak score on WHO Ordinal Scale for Clinical Improvement Peak score on modified Flu-PRO within the first 14 days
4. To test whether HCQ and HCQ + azithromycin decreases the resolution rate for symptomatic SARS-CoV-2 infection/COVID-19 disease compared to placebo	
 Proportion of days with fever after randomization Proportion of days with respiratory symptoms after randomization Proportion of days with SpO₂<93% without supplemental oxygen after randomization
5. To test whether HCQ and HCQ + azithromycin is associated with decreased viral shedding from self-collected nasal swabs over 14 days compared to placebo	
 Proportion of days with SARS-CoV-2 detected from mid-nasal swabs by PCR Quantity of SARS-CoV-2 detected from mid-nasal swabs by PCR

1.3. UPDATED OBJECTIVES AND ENDPOINTS

The trial was stopped early due to operational futility to meet the first two primary objectives (development of LRTI and hospitalization/death). In light of this several of the secondary endpoints have been updated as follows.

- Because of the very few number of hospitalizations, the Secondary Objective 2 will no longer be evaluated.
- The endpoint for Secondary Objective 3 will be the Flu-PRO score evaluated daily over 14 days instead of only the maximum value. Appropriate statistical methods will be detailed in Section 7.2.
- The CDC definition of COVID-19 will now define the endpoint for Secondary Objective (SO) 4. The endpoints currently presented in Table 1 for SO 4 will be summarized over time as described in Section 7.2.

1.4. RANDOMIZATION

Due to the adaptive design of the study, we implemented randomization to 12 dummy codes, stratified by site and risk cohort. Participants are randomized to 1 of 12 dummy codes that are mapped to active and control arms using an allocation ratio appropriate to the current design of the study. Participants were randomized 1:1:1 for the Hydroxychloroquine and Hydroxychloroquine + Azithromycin efficacy study.

1.5. SAMPLE SIZE AND POWER

When the protocol was written, we assumed that the trial would enroll quickly and therefore end a short time after starting, making interim analyses unattainable. Unfortunately, that has not been the case due to changes in the epidemic and controversy surrounding hydroxychloroquine. This SAP makes minor changes to the study design to allow for multiple interim looks at efficacy and futility and therefore includes minor changes to enrollment targets. The new sample size calculations are described here. All sample size calculations are based on 4 interim analyses with one final analysis and stopping rules for efficacy and futility.

1.5.1. LRTI and Hospitalization Endpoints

Overall sample size will depend on the number of events observed. To detect at least 50% treatment efficacy in reducing LRTI or hospitalization/death under a null hypothesis of no reduction, four interim monitoring analyses with stopping for futility and efficacy based on the O'Brien-Fleming bounds and 90% power, the trial is designed to achieve 93 events per pairwise comparison for the LRTI and hospitalization endpoints. For two active arms and one control arm, the total number of events required for each endpoint is 124.

As the initial sample size target, 165 per arm was chosen for each experimental group (HCQ, HCQ + azithromycin), assuming a control arm rate of approximately 30% and 5% dropout rate.

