11.1.1. COVID-19 Endpoints

Overall sample size will depend on the number of events observed. To detect at least a 1.5-fold increased risk of the COVID-19 symptom resolution rate under a null hypothesis of no reduction

and four interim monitoring analyses with stopping for futility and efficacy based on the O'Brien-Fleming bounds and 80% power, the trial is designed to achieve 99 events per pairwise comparison for the symptom resolution endpoints. To achieve this, 173 participants will be enrolled per arm.

As the initial sample size target, 210 per arm was chosen for each experimental group (HCQ, HCQ + azithromycin), assuming a control arm rate of approximately 30% and 5% dropout rate.

HR (active/control)	Events/arm	N per arm	Median control arm (days)	Median active arm (days)*
1.4	142	247	10	7
1.5	99	173	10	7
1.6	75	129	10	6
1.7	59	103	10	6
1.8	49	85	10	6
1.9	41	71	10	5
2,0	36	63	10	5

*Under constant baseline hazard assumption

11.1.2. *Viral Shedding Endpoint*

Assuming the median time to cessation of viral shedding is 10 days and a constant baseline hazard for cessation of shedding, approximately 62% of participants would no longer experience viral shedding at 14 days under the null hypothesis of no intervention effect. Assuming 420 participants per pairwise comparison, 90% statistical power, 1-sided type I error rate of 2.5% for efficacy, we can detect at least a 37% increase in the rate of cessation of viral shedding. Under an extreme example of having only half that sample, 210, we could detect an increase of 54% or higher.

11.2. *Populations for Analyses*

For analysis purposes, the following populations are defined and will be described in greater detail in the trial Statistical Analysis Plan:

Population	Description
Intention to Treat (ITT)	All enrolled participants
Modified ITT	All enrolled participants who do not have LRTI at Baseline: high-risk group for the primary clinical endpoint; high- and low-risk groups (separately) for the primary virologic endpoint.
PK evaluable	Participants from the DBS sub-study with at least 1 interpretable PK sample.

DBS: dried blood spot; PK: pharmacokinetic; PCR: polymerase chain reaction; SARS-CoV-2: severe acute respiratory syndrome coronavirus 2.

11.3. *Statistical Analyses*

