4.1.1. LRTI objective

Objective: To test the efficacy of HCQ and HCQ + azithromycin compared to placebo to prevent progression to LRTI, among persons with SARS-CoV-2 infection who are at high risk of progression.

Outcome: LRTI, defined by resting SpO₂<93%, sustained for 2 readings 2 hours apart AND presence of subjective dyspnea or cough within the first 14 days of follow-up.

Cohorts: mITT LRTI Cohort

Data Sets: HCQ LRTI Efficacy Data Set, HCQ+A LRTI Efficacy Data Set

Definition of Endpoint: A participant will be defined as having the endpoint if they have two resting SpO₂ readings less than 93% two hours apart but not more than 48 hours apart AND report subjective dyspnea (defined as a response of “somewhat or higher” on the “trouble breathing” question on flupro) or cough (defined as “somewhat or higher” as self-reported wet or dry cough) within 24 hours of the time the SpO₂ is reported during the first fourteen days of follow-up. The event time will be recorded as the day of the first SpO₂ reading less than 93% with the presence of subjective dyspnea or cough. Participants who do not reach this endpoint will be censored at the last time that the endpoint was ascertained not to be present. Hospitalization or death due to COVID-19 may be a competing risk. Per FDA guidance, participants who are hospitalized or die due to COVID-19 will have an event time that is the first of LRTI, hospitalization or death.

Analysis Details:

Kaplan-Meier cumulative incidence curves will be estimated and plotted for each intervention including 95% confidence intervals accounting for household cluster.

Cox proportional hazards models stratified by site and adjusted for baseline covariates identified above will be used to estimate the efficacy as 1 minus the hazard ratio. Due to potential clustering induced by the household design, robust standard errors will be estimated for the hazard ratio. The overall efficacy will be tested using a p-value ascertained from the Wald statistic based on

Confidential

the robust standard error. 95% confidence intervals will also be calculated based on the robust standard error. If there are too few endpoints to fit a Cox model then the proportion of participants meeting the endpoint in the first 14 days will be reported. Each active arm will be compared to the control arm separately using Fisher's Exact test.

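### SAP 1.5.1: 165 per arm is expected to give about 73 events per comparison, not the 93 to which the 90% power belongs

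*SAP*

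**What the plan says.** SAP 1.5.1 covers the LRTI and the hospitalization/death endpoints of the two hydroxychloroquine arms. The target effect is given as follows: "To detect at least 50% treatment efficacy in reducing LRTI or hospitalization/death under a null hypothesis of no reduction". The monitoring and power are "four interim monitoring analyses with stopping for futility and efficacy based on the O'Brien-Fleming bounds and 90% power". From these the SAP states that "the trial is designed to achieve 93 events per pairwise comparison for the LRTI and hospitalization endpoints" and that, for two active arms and one control arm, "the total number of events required for each endpoint is 124". The next paragraph reads "As the initial sample size target, 165 per arm was chosen for each experimental group", assuming a control arm rate of about 30% and 5% dropout.

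Four other places bear on this:
- SAP 1.5: "All sample size calculations are based on 4 interim analyses with one final analysis and stopping rules for efficacy and futility". It describes the resulting changes to the enrolment targets as minor.
- SAP 1.4: allocation was 1:1:1, so the control arm is also 165.
- SAP 4.1.1 fixes the effect scale for LRTI: the Cox models "will be used to estimate the efficacy as 1 minus the hazard ratio". SAP 4.1.2 compares proportions by Fisher's exact test for hospitalization/death.
- Protocol 11.1.1 still carries the figure for the same discontinued arms, at the same 30% and 5%: "As the initial sample size target, 210 per arm was chosen for each experimental group".

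**The concern.** An initial enrolment target is normally the number expected to deliver the required events under the stated assumptions. Here the rate, effect and dropout stand beside the event target, so a reader can multiply them out, and the product falls well short of 93. The protocol's 210, at the same rate and dropout, comes close. The SAP also says that interim looks were added. At a fixed effect and power that raises the maximum size, yet the target falls by 45 of 210, or 21%, without explanation.

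What is at stake is the public record of the design. A reader would take 165 per arm as the 90% power size and could carry that into the trial report.

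**Working it through.** **Inputs.** Control rate 0.30, dropout 5%, 165 per arm, 50% efficacy, 90% power, 93 and 124 events (SAP 1.5.1); five looks (SAP 1.5); 1:1:1 allocation (SAP 1.4). SAP 1.5.1 states no alpha, so I assume two-sided 5% from the general rule in SAP 2. I assume that dropouts contribute no events.

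**Step 1: reproduce 93.** Schoenfeld's formula at HR 0.5 gives 4 × (1.960 + 1.282)² / (ln 0.5)² = 87.5, or 88 events for a fixed design. Five O'Brien-Fleming looks multiply this by 1.026 (efficacy bounds only, 89.8 events) to 1.091 (efficacy and binding futility bounds, 95.5 events). The stated 93 lies inside that range and implies an inflation of 93 / 87.5 = 1.063. The total of 124 fits as 62 control + 31 + 31. So the event targets are sound, and they rest on HR 0.5.

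**Step 2: expected events at 165 per arm.** Participants retained per arm: 165 × 0.95 = 156.75.

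| Reading of 50% efficacy | Active rate | Events per comparison | Three-arm total |
|---|---|---|---|
| HR 0.5 | 1 − 0.7^0.5 = 0.163 | 156.75 × 0.463 = 72.6 | 156.75 × (0.300 + 2 × 0.163) = 98.2 |
| Risk halved | 0.15 | 156.75 × 0.45 = 70.5 | 156.75 × 0.60 = 94.1 |
| Stated | – | 93 | 124 |

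The shortfall is 22–24% per comparison and 21–24% in total. With no dropout at all the pairwise counts are 76.5 and 74.2. For 165 per arm to give 93 events the control rate would have to be about 38% (HR 0.5) or 40% (risk halved).

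**Step 3: power if enrolment ended at 165 per arm, keeping each scale to itself.**
- *HR 0.5, 72.6 events.* Fixed design: √(72.6/4) × 0.693 − 1.960 = 0.99, or 84%. Five-look O'Brien-Fleming, efficacy only: 83%. With the SAP's implied inflation (72.6 / 1.063 = 68.3 effective events): 82%. With binding futility bounds: 81%.
- *Risk halved, 70.5 events.* The equivalent HR is ln 0.85 / ln 0.70 = 0.456. Five-look, efficacy only: 90%. With the implied inflation: 89%. Two-proportion formula: 89%. On this scale, however, the matching target is 4 × (1.960 + 1.282)² / (ln 0.456)² × 1.063, or about 72 events, not 93.

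**Step 4: size expected to give 93 events.** At HR 0.5: 93 / (0.95 × 0.463) = 211 per arm. The protocol's 210 gives 199.5 × 0.463 = 92.4 events at HR 0.5, or 199.5 × 0.45 = 89.8 if risk is halved.

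**Step 5: a possible origin of 165.** A fixed two-proportion calculation of 30% against 15%, two-sided 5%, 90% power and unpooled variance gives (0.21 + 0.1275) × (1.960 + 1.282)² / 0.15² = 157.6. Divided by 0.95 this is 166. It makes no allowance for the interim looks and does not lead to 93 events. The documents do not say how 165 was obtained.

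**The case against.** Three points can fairly be made for the SAP.

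- **The design is event-driven.** SAP 1.5.1 opens by making the overall size depend on observed events and calls 165 an initial target. Power would have stayed at 90% had enrolment run on to 93 events. This stands, and it means the 82–83% is conditional on ending at 165 per arm. It does not explain why 165 was the starting figure, since the stated assumptions do not lead from it to 93.
- **The efficacy scale is not named in SAP 1.5.1.** If 50% efficacy means halved risk, 165 per arm has close to 90% power by the log-rank calculation, and about 87% by the Fisher's exact test planned for hospitalization/death. This also stands, so a single power figure without its scale would be wrong. But that reading gives up 93 and 124 as event targets, so the section still mixes two bases.
- **A changed target is announced.** SAP 1.5 says that enrolment targets were revised, so differing from 210 is not an error in itself. What is missing is the reason for a reduction when looks were being added.

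A reader might infer more than the documents support. Putting 30% in both arms at 165 gives 156.75 × 0.60 = 94 events, which suggests that the treatment effect was left out. The calculation in Step 5 reaches 165 equally well, so that diagnosis is not established. Nor should the halved-risk event rate be combined with the target of 93: the result, 93 / (0.95 × 0.45) = 218 per arm, mixes two effect scales.

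**Conclusion.** The inconsistency is real and lies within one section. Under SAP 1.5.1's own rate, effect and dropout, 165 per arm gives about 71–73 events per comparison against 93, and 94–98 in total against 124. That shortfall holds on either reading of efficacy and with or without dropout.

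The consequence for power depends on the scale. At HR 0.5, which reproduces 93 and agrees with SAP 4.1.1, power at 165 per arm is about 82–83% instead of 90%, assuming two-sided 5% and five O'Brien-Fleming looks. With halved risk it is about 89–90%. It would go too far to say that the trial was simply underpowered at 165: that holds on only one of the two readings, and only if enrolment had been fixed there.

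The practical weight is limited. SAP 5 records that enrolment stopped for operational futility and that no interim analyses were performed, so no analysis or enrolment decision turns on this. It should still be corrected, because the stated size does not deliver the stated design.

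**What to change.** Rewrite SAP 1.5.1 on one named effect scale, and state the alpha used. Either:
- keep 165 per arm, and state about 73 expected events per comparison and about 82–83% power at HR 0.5 if enrolment ends there; or
- keep 93 events, and give about 211 per arm as the size expected to reach it at HR 0.5.

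In both cases, state that 90% power belongs to reaching 93 events and not to 165 per arm. Say how 165 was derived, and explain the change from the protocol's 210, which gives 90–92 events on the same rate and dropout.

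The cost is a few sentences in the SAP and, under the first option, a less favourable stated power. No further enrolment is implied, because this stage has stopped.
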